These initial results served as a basis for generating additional hypotheses. They were presented as oral communication at the congress of the Spanish Society of Medical Oncology on October 18, 2022 and accepted to be presented at the poster session of the annual congress of the American Society of Clinical Oncology ASCO on June 5, 2023.

Experience of the group of researchers in projects led by [name]:

- IPT-2011-1569-01000. Valorization of oncological biomarkers for the development of diagnostic/prognostic kits for prostate and lung cancer
- PI13/01806. Image Re-Analysis Study and Correlation Between Metabolic Changes Targeted by PET/CT and Known Mutations in Non-Small Cell Lung Cancer (NSCLC)
- PI18/01778. "Predictive Value of Treatment Response of CB2 Expression in Colon Cancer" (Co-PI)
- H2020-SC1-2016-2017 (Personalized Medicine). IASIS. Integration and analysis of heterogeneous big data for precision medicine and suggested treatments for different types of patients.
- RTC-2017-6502-1. INmunoSIGHT- Immunological and molecular characterization in liquid biopsy of patients with lung cancer for immunotherapy.
- H2020-875160 CLARIFY. Cancer Long Survivors Artificial Intelligence Follow up.
- P4 LUCAT. Personalized medicine for lung cancer treatment: using Big Data-driven approaches for decision support.

Experience of the principal investigator:

- H2020-875160 CLARIFY. Cancer Long Survivors Artificial Intelligence Follow up.
- P4LUCAT. Personalized medicine for lung cancer treatment: using Big Data-driven approaches for decision support.
- Author and principal investigator of the national registry of the Colombian Association of Hematology and Oncology ACHO of patients with cancer and Covid 19 infection (ACHOC-C19). 2020-2022.
- Author and principal investigator of the Epidemiological Registry of Malignant Melanoma in Colombia (REMMEC) of the Colombian Association of Hematology and Oncology ACHO. 2021- present.

5. Funding

The financing of the project will be supported by the promoter of the study, the GECP Foundation.

6. Objective and justification of the research based on the most up-to-date review of the available scientific evidence.

Theoretical framework

The population of cancer survivors may suffer long-term alterations secondary to antineoplastic treatments that lead to the deterioration of their quality of life and that include the generation of sexual dysfunction (SD).

Most of the data on SD in cancer patients come from patients with breast cancer, gynecologic neoplasms, and prostate cancer, most of whom receive hormonal cancer treatments and cytotoxic chemotherapy, and have often undergone mutilating cancer surgeries.

There are limited prospective studies carried out with heterogeneous collection instruments, which does not allow obtaining adequate and complete information on the real situation of the problem.

As a source of local data, there is a study to characterize sexual dysfunction in a cohort of cancer survivor patients derived from the European CLARIFY H2020 project (Cancer Long Survivor Artificial Intelligence Follow-Up) that we carried out at the Puerta de Hierro University Hospital from May 2020 to May 2022.

A total of 383 patients were included, distributed according to diagnosis in breast cancer 68.1% (261), lung cancer 26.3% (101) and lymphomas 5.48% (21).

Globally, 69% of men vs. 31% of women reported being sexually active and 76% of women vs. 24% of men had general sexual dissatisfaction.

In our study, the largest sample of patients was women with breast cancer (261), which corresponds to the highest overall frequency reported in the literature of this type of neoplasm.

In relation to the stage, patients with early breast cancer treated and followed up receiving hormonal therapy showed a greater tendency to suffer moderate disorders of the phases of sexual response, while patients with a diagnosis time greater than 5 years showed a tendency to not present alterations. Statistically significant associations were confirmed in patients with metastatic breast cancer to present severe disorders of the phases of sexual response.

Regarding the specific characteristics of patients with lung cancer, which represented a smaller sample size (101), 66.3% (67) were men, the median age was 64 and 61 years in men and women respectively. 45% of women and 41% of men reported being sexually active. The absolute frequency of overall sexual dissatisfaction was 8.8% in men vs. 2.8 in women.

Men showed a tendency to develop severe alterations in the phases of sexual response. On the other hand, a statistically significant association was evidenced for severe sexual response disorders in women. Of these, 35.2% received chemotherapy, 26.4% immunotherapy and 20.5% targeted therapies.

When looking for similar information in the literature, we found previous research in women with lung cancer that supports that 95% of these patients score below the 50th percentile when rating their sexual function and a 2022 study, in which 64% had metastatic disease, and almost half were receiving targeted therapy, finding that 77% reported moderate to severe sexual dysfunction.

Our data obtained in patients with lung cancer, despite representing a small sample size, suggest that SD is an alteration that is significantly affecting the quality of life of this population.

In addition, they suggest that there is a potential role for new cancer treatments such as targeted therapy and immune checkpoint inhibitors in the development of DS, for which there is limited information

Justification

Given the increase in lung cancer survivors and the therapeutic options different from those historically described as associated with DS, added to the fact that the patient profile has changed in recent years, with the male gender remaining the most affected, but with a significant increase in diagnosis in women and younger and non-smoking patients; it is important to characterize SD in this population and determine its severity as well as the associated risk factors and the role of new antineoplastic therapies.

This knowledge will make it possible to propose strategies for approaching and monitoring cancer that help improve the quality of life of these patients during and after cancer treatments.

A study is planned to be carried out with a larger number of patients with lung cancer, including the population of Spain and Latin American countries to obtain a sample of more diverse and heterogeneous characteristics, with clinical, cultural and sociodemographic differences. This will allow us to obtain better and greater data and consequently to define the clinical and treatment factors significantly associated with SD in these individuals and to obtain a more complete view of the reality of the problem.

The results of this research will make it possible to carry out interventions specifically aimed at this population and modify the oncological follow-up guidelines currently in force. Likewise, the information collected will serve as a basis for generating new protocols for a multidisciplinary approach including the participation of psychology and specialists in urology, gynecology and psychiatry.

Additionally, the knowledge obtained will allow to generate education about SD to the entire treating medical team and patients to overcome the barriers that prevent adequately addressing this condition.

7. General Objective

To identify and describe the type, frequency, and severity of SD in patients with lung cancer and to generate targeted clinical approach and oncological follow-up strategies based on specific findings in this population.

8. Secondary Objectives

- Describe the clinical, cultural, and sociodemographic characteristics of the study population.
- To characterize differences in sexual dysfunction in patients with lung cancer according to age, sociodemographic characteristics, region of residence, and type of cancer treatment.
- Identify risk factors for the development and severity of sexual dysfunction.
- To promote education and awareness among the health team on the identification and characteristics of sexual dysfunction in patients with lung cancer.
- To collect information to generate recommendations for the multidisciplinary approach and management of sexual dysfunction during oncological follow-up applicable to current oncology practice.
- To propose education strategies on the management of sexual dysfunction in patients with lung cancer aimed at patients and their families.
- To generate a collaborative network of Ibero-American research.

9. Methods and procedures envisaged, including statistical and other analytical tests

The recruitment will be carried out from July 2023 and will be carried out until December 2023, the analysis of the information will be carried out from January to March 2024.

Clinical and demographic variables (Annex 1) will be collected by the treating oncologists and recorded in an electronic data collection notebook designed for this study, which will be accessed through a personal username and password.

Data anonymization will be ensured for all patients. To this end, they will identify themselves with a numerical code in order to respect the confidentiality of personal data. The patient's initials and medical record number will be separated from the rest of the data and will not be included in the study database.

Measurements of sexual function will be performed through an electronic survey that will be sent to patients who agree to participate in the study and sign the informed consent. This electronic survey will be hosted on an exclusive study platform, which the patient will enter through a user corresponding to the anonymization numerical code and a personal password assigned after signing the informed consent.

The survey will consist of single-choice questions based on two validated questionnaires to explore and diagnose sexual dysfunction in women (FSM) and men (FSH) separately, which have been evaluated and translated into Spanish by a local research group in the Valencian Community and are available for use in the primary care setting in Spain. These instruments were selected because of the possibility of self-administration, their history of efficacy in assessing complete sexual function in the general population, and their low level of complexity. Through this instrument, criteria of the phases of sexual response according to DSM V (FSH) and DSM IV (FSM) will be evaluated, as well as a descriptive parameter of sexual activity. (Appendices 2 and 3)

The information entered by patients will only be visible by the principal investigator, who will have a personal username and password to access the data.

10. Statistical analysis

A descriptive analysis of the variables will be carried out; for the characteristics a univariate analysis. The qualitative variables will be determined with absolute and relative frequencies and the quantitative variables by measures of central tendency and dispersion, with mean and standard deviation for those with normal and median distribution and interquartile range for those with non-normal distribution. Subsequently, an inferential analysis will be performed, with chi2 distribution to evaluate the correlations between the different variables and the main outcomes in the measurement of sexual function.

Possible trends in association between variables and outcomes will be evaluated and the main trends described will be carried out through a multivariate analysis.

Logistic regression analyses will be performed to determine risk factors

Statistical analyses will be carried out using the SPSS Statistics 20 or R program.

11. Full project overview in understandable language

The population of cancer survivors may suffer long-term alterations secondary to antineoplastic treatments that lead to the deterioration of their quality of life and that include the generation of sexual dysfunction (SD). Most of the data on SD in cancer patients come from patients with breast cancer, gynecologic neoplasms, and prostate cancer, most of whom receive hormonal cancer treatments and cytotoxic chemotherapy.

According to data from recent institutional research on the characteristics of SD in cancer survivors, it was documented that patients with lung cancer have a high frequency of DS, which is significantly affecting their quality of life.

Given the increase in survivors of this type of neoplasm and the fact that the patient profile has changed in recent years with a significant increase in diagnosis in women and younger and non-smoking patients; In addition to the fact that cancer treatment is different from that usually related to SD generation, it is of great importance to characterize SD in this population and determine its severity as well as the associated risk factors and the role of new antineoplastic therapies.

This knowledge will make it possible to propose strategies for approaching and monitoring cancer that help improve the quality of life of these patients during and after cancer treatments.

Likewise, the information collected will serve as a basis for generating new protocols for a multidisciplinary approach and will generate education about SD for the entire treating medical team as well as for patients and their families.

12. Participants, Consent and Information

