12.2 Criteria for the inclusion/exclusion of research participants

Inclusion criteria

- Age greater than or equal to 18 years and less than or equal to 70 years.
- Diagnosis of lung cancer stages IB to IV.
- Have received systemic cancer treatment for at least 3 months or be under cancer follow-up after having received systemic therapy for at least 3 months with stable tumor disease or in partial or complete response on imaging.
- ECOG ≤ 2

Exclusion Criteria

- Patients with comorbidities (kidney failure, cardiovascular diseases or similar) not controlled with corresponding medical management.
- Individuals with physical disability or cognitive impairment that prevents them from completing the electronic data collection form.

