12.4 Study modality: open, single-blind or double-blind

Analytical cross-sectional observational study.

12.5 Deadlines and details of information for potential research participants, including proposed methods for communicating such information.

Not applicable

12.6 Documentation, visual or other material to be used in the request for consent, or, in the case of persons unable to consent, for authorisation to participate in the research

1. Patient information sheet that will contain the relevant and necessary information for the patient to decide if they want to participate in the study. (Annex 4)
2. Informed consent (Annex 5), which each researcher must explain to the patient as completely as possible, specifying in understandable language the characteristics of the research project.

12.7 Provisions to ensure respect for the privacy of research participants and to ensure the confidentiality of personal data

The study will be conducted in accordance with the Good Clinical Practice (GCP) Standards.

The confidentiality of the data will be guaranteed in accordance with the provisions of Organic Law 3/2018, of 5 December, on the Protection of Personal Data and guarantee of digital rights and will separate personal clinical data in accordance with current legislation (Law 14/2007, of 3 July, on biomedical research).

All patients' data will be anonymized. To this end, the patient will be identified by means of a numerical code in order to respect the confidentiality of the patients' personal data. The patient's initials and medical record number will be separated from the rest of the data, not included in the study database.

Access to personal information will be restricted to the study investigators, the HUPHM clinical research ethics committee and specialized personnel authorized to verify the data and procedures of the study, always maintaining the confidentiality of the latter in accordance with current legislation.

The informed consent will be written in Spanish and in understandable language.

Subjects participating in the study may withdraw their consent to the use of their data in the analysis at any time, without giving a reason and without incurring any liability or loss.

12.8 Forecasts for the processing of information that may be generated during research and of relevance to the present or future health of participants and members of their families

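### Secondary objective 3 asks for risk factors for the development of sexual dysfunction, but a cross-sectional post-treatment survey supports only associations with dysfunction present at the survey, unless an annex records onset

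*Combined protocol and SAP*

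**What the plan says.** Section 8 lists seven secondary objectives. The third is to "Identify risk factors for the development and severity of sexual dysfunction".

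Section 12.4 gives the design as "Analytical cross-sectional observational study". Section 9 states: "Measurements of sexual function will be performed through an electronic survey that will be sent to patients who agree to participate". The questionnaires are described there as covering the phases of sexual response, plus a descriptive parameter of sexual activity. No repeat survey and no question on onset is mentioned. Section 12.2 requires patients to "Have received systemic cancer treatment for at least 3 months or be under cancer follow-up", and the follow-up route also requires at least 3 months of earlier systemic therapy. Section 12.9 says that clinical data come from the medical history.

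Section 10 plans chi-square tests, says "Possible trends in association between variables and outcomes will be evaluated", and adds "Logistic regression analyses will be performed to determine risk factors". It gives the regression no outcome definition and no time reference.

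Elsewhere the wording is milder. Sections 6 and 12.8 aim to "define the clinical and treatment factors significantly associated with SD in these individuals". The justification in section 6, repeated in the lay summary in section 11, wants to "determine its severity as well as the associated risk factors and the role of new antineoplastic therapies".

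**The concern.** Development means that SD arises in someone who did not have it before. To study that, one needs to know who was free of SD at some starting point, or when SD began. The main text describes neither. Every participant is surveyed after at least 3 months of treatment, so the survey itself cannot supply a pre-treatment value.

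Treatment does come before the survey; that order is not in doubt. What is unknown is whether SD came before treatment or diagnosis. SD found at the survey is therefore a mixture of older SD that has persisted and SD that is new.

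Followed as written, the plan could report a prevalence odds ratio as a risk factor for developing SD. This matters most for treatment, because sections 6 and 11 ask about the role of newer therapies and section 12.8 expects the results to support interventions and proposed changes to follow-up guidelines.

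**Working it through.** The plan has no figure of its own to reproduce: it gives no pre-treatment SD rate, onset rate or effect size. The mismatch follows from setting sections 8, 9, 10, 12.2 and 12.4 side by side. The arithmetic below shows only how far the two odds ratios can differ. **All inputs are assumptions, and the odds ratios are crude.**

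Let p0 be the proportion with SD before treatment, r the proportion of that prior SD that has remitted by the survey, and i the onset proportion among those without prior SD. Then

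- prevalence at the survey: P = p0(1 − r) + (1 − p0)i
- prevalence odds ratio, group B vs A: [P_B/(1 − P_B)] / [P_A/(1 − P_A)]
- onset odds ratio: [i_B/(1 − i_B)] / [i_A/(1 − i_A)]

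**1. A real difference in onset, with the groups otherwise alike.** Take i = 0.20 in A and 0.40 in B. The onset odds ratio is (0.40/0.60)/(0.20/0.80) = 2.67. With p0 = 0.30 and r = 0 in both groups, P_A = 0.30 + 0.70 × 0.20 = 0.44 and P_B = 0.30 + 0.70 × 0.40 = 0.58. The prevalence odds ratio is (0.58/0.42)/(0.44/0.56) = 1.76. Over the grid:

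| p0 (both groups) | r = 0 | r = 0.2 | r = 0.4 |
|---|---|---|---|
| 0.30 | 1.76 | 1.77 | 1.81 |
| 0.40 | 1.64 | 1.62 | 1.64 |
| 0.50 | 1.56 | 1.50 | 1.50 |

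The range is 1.50 to 1.81 instead of 2.67. No imbalance between groups is needed for this.

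**2. No difference in onset, unequal prior SD.** Take p0 = 0.30 vs 0.50, i = 0.40 in both and r = 0. P = 0.58 vs 0.70, odds ratio 1.69. Over i = 0.20 to 0.40 and r = 0 to 0.40 the range is 1.17 to 1.91. For a 5-point imbalance (37.5% vs 42.5%) it is 1.04 to 1.17.

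**3. A real onset odds ratio of 2.67, with prior SD commoner in the low-onset group.** Take p0 = 0.50 in A and 0.30 in B. With r = 0, P = 0.60 vs 0.58, odds ratio 0.92. With r = 0.4, P = 0.40 vs 0.46, odds ratio 1.28.

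**4. No difference in onset, equal prior SD, unequal remission.** Take p0 = 0.40 and i = 0.30 in both, r = 0 vs 0.40. P = 0.40 + 0.18 = 0.58 vs 0.24 + 0.18 = 0.42. The odds ratio (higher over lower) is (0.58/0.42)/(0.42/0.58) = 1.91.

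**When the two agree.** If p0 = 0 in both groups, P = i and the odds ratios coincide. If p0, r and i are all equal between groups, both are 1.00. The correct statement is that they need not be equal.

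**The case against.** The best defence is that this is one word in one of seven secondary objectives. The design is openly labelled cross-sectional, and most stated aims are associational. The protocol also uses the verb loosely: section 6 says that men in the earlier survey showed a tendency to develop severe alterations. The objective may mean no more than presence of SD. That argument limits the weight of the point, but it also supports rewording, since the looser meaning is what the design can deliver.

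Objective 3 does not mention treatment; the link comes from sections 6 and 11, which speak of a role and not of onset. This is fair. The mismatch applies equally to any other factor in the regression, and treatment is only where a misreading would cost most.

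The illustration is not calibrated to this population. The modelled prevalences run from 32% to 70%, while section 6 cites 77% with moderate to severe SD in an earlier study. Adjustment in the multivariate models may also remove part of any imbalance. Both points stand as limits on the numbers. Adjustment for other covariates does not, however, turn an outcome of SD present into an outcome of SD newly arisen.

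The annexes may record onset or prior function. This cannot be settled here. Such an item would be retrospective, and section 10 does not say how it would be used.

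Section 12.8 calls the evidence prospective, which might suggest follow-up. No repeat measurement is described anywhere in the main text.

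**Conclusion.** The point holds, and it is limited. On the main text, the regression estimates associations with SD present at the survey and not risk factors for its development. This is conditional on the annexes not recording onset or prior function. The size depends wholly on assumed inputs: with equal prior SD of 30-50% and equal remission of 0-40%, an onset odds ratio of 2.67 would show as 1.50 to 1.81.

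A reader might infer more, and the documents do not support it:

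- *That the treatment associations will be biased.* Nothing shows that prior SD or remission differs by treatment.
- *That equal prior SD removes the risk of a false signal.* Case 4 shows that remission must also be alike.
- *That the whole plan claims causation.* The general objective, objective 2 read as description, and the severity half of objective 3 read as association with current severity are unaffected.

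The correction is worth making because it changes what may be concluded; it does not call the study itself into question.

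**What to change.** 1. In section 8, reword objective 3: *identify factors associated with the presence and severity of SD at the time of the survey*.
2. In section 10, restate the aim of the logistic regression as *to identify factors associated with SD*, and add: *Odds ratios are prevalence associations and will not be reported as effects on the development of SD.* If an annex item does record onset or prior SD, state instead how the regression uses it.

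This needs no new data and no change of model. The cost is a weaker permitted conclusion about what leads to SD and possibly a wording amendment, since section 12.1 submits the protocol to the ethics committees of the participating institutions. Section 9 schedules analysis for January to March 2024. If the change comes after the analysis, it should be dated and declared as such.

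### Does section 10 need to say whether sexually inactive patients count in the denominator of the sexual dysfunction frequencies?

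*Combined protocol and SAP*

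**What the plan says.** Section 7 sets the general objective: "To identify and describe the type, frequency, and severity of SD in patients with lung cancer".

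Section 9 describes two self-administered questionnaires, one for women (FSM) and one for men (FSH). They assess the phases of sexual response "as well as a descriptive parameter of sexual activity". Section 9 points to Appendices 2 and 3 for the instruments; those appendices are not in the supplied text.

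Section 10 gives the descriptive analysis: "The qualitative variables will be determined with absolute and relative frequencies". It then plans an inferential analysis "with chi2 distribution to evaluate the correlations between the different variables and the main outcomes in the measurement of sexual function", followed by multivariate and logistic analyses. It does not define the main outcomes, state a denominator or mention sexually inactive respondents.

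Section 12.2 lists eligibility by age, stage, systemic treatment, performance status, comorbidity and ability to complete the form. Sexual activity is not a criterion.

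Section 6 (theoretical framework) reports the investigators' lung pilot of 101 patients, 67 of them men: "45% of women and 41% of men reported being sexually active".

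**The concern.** A frequency means little without its base, and here the base is not written down for the quantity that the general objective asks for. The group left unmentioned is not marginal: on the pilot's rates most patients were inactive. A questionnaire about phases of sexual response may be hard for an inactive person to answer. One analyst might therefore report a phase disorder as a share of all respondents and another as a share of those who could be scored. Both would be following section 10, and a reader could not tell the two results apart. The same question carries into the chi-square tests and the logistic models.

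**Working it through.** **Inputs (section 6).** Lung pilot 101 patients; men 67; women 101 − 67 = 34. Active: 45% of women, 41% of men.

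**Step 1: reproduce the pilot's own figure.** 67/101 = 66.3% men, as printed.

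**Step 2: inactive share.** Active = (0.45 × 34 + 0.41 × 67)/101 = (15.30 + 27.47)/101 = 42.77/101 = 42.3%. Inactive = 57.7% (55% of women, 59% of men).

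**Step 3: whole patients.** 15/34 = 44.1% and 16/34 = 47.1%; 27/67 = 40.3% and 28/67 = 41.8%. None rounds to the printed rates. Taking 42 to 44 active patients gives 58.4% down to 56.4% inactive. If the two rates were swapped between the sexes they would fit: 14/34 = 41.2% and 30/67 = 44.8%, so 57/101 = 56.4% inactive. Roughly 56% to 58% is a fair range.

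**Step 4: size if inactive patients are unscored on a phase.** Suppose one analyst keeps them in the denominator as non-cases and another drops them. The ratio of the two results is 1/0.423 = 2.36 overall, or 1/0.45 = 2.2 in women and 1/0.41 = 2.4 in men. With assumed rates of dysfunction among active patients:

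| Assumed rate in active patients | Same cases over all respondents |
|---|---|
| 30% | 0.30 × 0.423 = 12.7% |
| 50% | 0.50 × 0.423 = 21.2% |
| 77% | 0.77 × 0.423 = 32.6% |

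The 77% is the moderate-to-severe figure that section 6 cites for women with lung cancer. The other two rates are illustrative.

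**Step 5: size if everyone is scored on every phase.** Scored respondents and all respondents are then the same people. The ratio is 1 and nothing is ambiguous.

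**Step 6: risk-factor results.** Assume 50% dysfunction in active patients and compare men with women (41% and 45% active). Counting every inactive patient as a case gives men 0.59 + 0.205 = 0.795 and women 0.55 + 0.225 = 0.775, so the odds ratio is (0.795/0.205)/(0.775/0.225) = 1.13. Counting none gives (0.205/0.795)/(0.225/0.775) = 0.89. Even these extreme codings, which the plan does not propose, move the odds ratio little.

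**Step 7: what base do the documents imply?** The objective's population is patients with lung cancer. Section 12.2 admits patients whatever their activity. Section 10 excludes no one and defines no subset. Read together, the base is all respondents.

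**The case for a change.** The best case for a change is that the remedy costs a few sentences and one table, while the quantity affected is the general objective itself. A scoring rule in an appendix says how one person is scored; it need not say which denominator a published percentage uses. That is true, and it is why the gap is real.

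The pilot might also be offered as proof that a base can go missing. It states: "The absolute frequency of overall sexual dissatisfaction was 8.8% in men vs. 2.8 in women". Against bases of the same sex neither figure fits:

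- Men: 6/67 = 8.96%; 2/27 = 7.4% and 3/27 = 11.1%; 2/28 = 7.1% and 3/28 = 10.7%.
- Women: 1/34 = 2.94%; 1/15 = 6.7%; 1/16 = 6.25%.

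But 3/34 = 8.82%, so 8.8% does fit all 34 women, which suggests swapped sex labels; the 2.8% still fits neither sex (2/67 = 2.99%). Another reading is a truncated share of all 383 pilot patients: 34/383 = 8.88% and 11/383 = 2.87%. Section 6 does truncate elsewhere (101/383 = 26.37%, printed as 26.3%). That match is weak evidence, because steps on a base of 383 are only 100/383 = 0.26 points and many one-decimal values will fit. What stands is that the pilot was reported unclearly. It does not show that section 10 would lead to a wrong result. The outcome is overall dissatisfaction, which section 6 reports separately from phase disorders and which is not shown to depend on phase scoring.

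The same holds for "Globally, 69% of men vs. 31% of women reported being sexually active". At most 67 + 21 = 88 pilot patients were men, and with 41% of the 67 lung men active the male rate cannot exceed (27.47 + 21)/88 = 55%. This is a reporting problem in an earlier mixed-cancer study.

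An active-only result is also no clear gain. Its intervals would be 1/√0.423 = 1.54 times as wide, and it selects on something that dysfunction can cause. If true dysfunction were 60%, with inactivity 70% in those affected and 40% in the rest (assumed values), active patients would show 0.6 × 0.3/(0.6 × 0.3 + 0.4 × 0.6) = 43%.

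**Conclusion.** No change to the plan follows. Section 10 leaves the denominator unstated, and roughly 56% to 58% of the lung pilot were inactive. Sections 7, 10 and 12.2 together already point to all respondents, which is the base one would want as the main result. Stating it would record the natural reading and correct nothing. The factor of 2.4 applies only if the questionnaires leave inactive patients unscored on a phase and analysts then treat them differently; if everyone is scored, it is nil. The effect on risk-factor results is small even under extreme codings (odds ratio 1.13 or 0.89). Because activity is recorded, a breakdown by activity and the number scored on each phase can be shown in the report without a protocol change.

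This rests on three assumptions: that the printed 45% and 41% are shares of all 34 women and 67 men; that the pilot, from one hospital, says something about the new Spanish and Latin American sample; and that Appendices 2 and 3 contain the usual scoring instructions. If those instructions proved silent on inactive respondents, the report would need to state its handling of them, which is ordinary good practice.
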